4 INTRODUCTION AND RATIONALE

4.1 INTRODUCTION

Human acid sphingomyelinase deficiency (ASMD) is a serious, rare, life threatening lysosomal storage disorder for which only palliative treatment exists. Patients with ASMD are unable to metabolize sphingomyelin properly due to mutations in SMPD1, the gene encoding acid sphingomyelinase (ASM), whose transcription and translation results in a defective (ASM) enzyme. Inactivity of ASM leads to the lysosomal accumulation of sphingomyelin and, secondarily, increases in cholesterol and other related lipids, mostly in the organs, such as the spleen, liver, lung, and bone marrow.

Historically, ASMD has been diagnosed as Niemann-Pick Disease (NPD) and of either Type A or Type B disease. Type A (NPD A) is characterized as the early-onset and acute neuropathic form of (NPD) and results in failure to thrive, hepatosplenomegaly, rapidly progressive neurological degeneration, and death, usually before the age of 3 years (1). Niemann-Pick disease Type B (NPD B) is a milder disease with little or no neurological involvement that may already have manifestations in childhood. The most common disease manifestation is hepatosplenomegaly. Other more variable features include liver dysfunction, pulmonary disease, retinal stigmata, and growth retardation. Niemann-Pick disease Type B is usually diagnosed in childhood after organomegaly is observed, typically after the age of 2 years. Most patients diagnosed with Type B disease live into adulthood. Being an autosomal recessive single gene disease, ASMD is acknowledged to generate a spectrum of phenotypes. Accordingly, cases classified as intermediate to the A and B extremes have been reported. Patients with this intermediate form (NPD A/B) may develop neurologic symptoms during childhood and have a chronic neurodegenerative disease course.

Sanofi Genzyme is developing a potential enzyme replacement therapy for ASMD with olipudase alfa, a recombinant human acid sphingomyelinase, for the treatment of the non-neurological manifestations of ASMD. This recombinantly-derived enzyme is expressed in Chinese hamster ovarian cells transfected with olipudase alfa complementary DNA that encodes a 627-residue peptide chain. The resulting gene product retains the enzymatic activity and lysosomal targeting of the native protein.

Proof of concept for olipudase alfa therapy has been demonstrated in the acid sphingomyelinase knock-out (ASMKO) mouse (2), which exhibits both systemic and neurological features of ASMD. Repeat intravenous (IV) bolus administration of olipudase alfa to ASMKO mice led to dose-dependent reductions of sphingomyelin in visceral organs and in the lungs to a lesser extent, but was unable to prevent neurologic decline and prolong survival (3, 4). However, chronic dosing in the ASMKO animal model is limited because the mice succumb to the neurologic disease resulting from the natural progression of complete ASMD in approximately 6 to 8 months.

Pharmacodynamic (PD), pharmacokinetic (PK), and toxicological studies conducted in the ASMKO mouse found significant reductions of sphingomyelin in the liver, lung, kidney, and spleen at olipudase alfa doses ranging from 0.1 to 5.0 mg/kg in a time-dependent manner;

however, toxicity was observed in ASMKO mice given single high-dose boluses of olipudase alfa (≥ 10 mg/kg). The same single, high doses did not cause toxic effects in normal mice, Sprague Dawley rats, or cynomolgus monkeys, suggesting that catabolites of sphingomyelin, and not olipudase alfa itself, were the cause of the toxic effects. Subsequent “debulking” studies in ASMKO mice demonstrated that a slow reduction in the sphingomyelin load over time using multiple low doses of olipudase alfa (4 doses of 3.0 mg/kg of olipudase alfa administered over 8 days) followed by a high dose (20 mg/kg 3 days later) prevented the toxicity associated with the single initial high doses. These findings suggest that the observed toxicity is related to the rate of substrate degradation and that step-wise removal of substrate likely mitigates toxicity. Furthermore, repeat high doses of olipudase alfa (30 mg/kg every 2 weeks for 7 doses) administered after a 7-day debulking period (3 mg/kg on Days 1, 3, 5, and 7) also did not cause toxicity.

During clinical development of olipudase alfa, incremental changes were made to the olipudase alfa manufacturing process. The different processes are referred to as Process B, C(█) and C(█).

In a completed Phase 1 study (5), the safety, PK, and PD profiles of single, ascending doses of olipudase alfa were evaluated. Single doses of 0.03, 0.1, 0.3, 0.6, and 1.0 mg/kg of olipudase alfa were infused sequentially by dose cohort in 11 adult patients with ASMD. Study results found dose-related increases in ceramide, bilirubin, high-sensitivity C-reactive protein (hsCRP), and other acute phase reactants in patients that peaked 24 to 48 hours postdose and resolved by Day 14. Reported adverse events (AEs) involving constitutional symptoms (pain, fever, nausea, and vomiting) were consistent with first-dose-related toxicity and occurred in a dose-dependent fashion as was previously observed in the ASMKO mouse. Serious adverse events (SAEs) related to olipudase alfa treatment were not reported. The sponsor terminated the study subsequent to a single patient dosed at 1.0 mg/kg of olipudase alfa presenting with hyperbilirubinemia and an acute-phase reaction (APR) with clinical symptoms. Of note, this patient was subsequently confirmed to have Gilbert’s syndrome. Because there were no other signs of liver toxicity or hemolysis, the observed hyperbilirubinemia may have been secondary to specific inhibition of bilirubin uptake into hepatocytes and/or glucuronide conjugation of bilirubin within hepatocytes.

In a completed Phase 1b, open-label, multicenter ascending-dose study in 5 adult patients with ASMD, the safety and tolerability of olipudase alfa were evaluated during a 26-week treatment period (6). Patients received an initial IV dose of 0.1 mg/kg of olipudase alfa, then the dose was escalated in a stepwise manner to a final target IV dose of 3.0 mg/kg. All patients remained at 3.0 mg/kg for the remainder of the treatment period. Upon completion of the study, all patients enrolled into an open-label, long-term treatment study. Results from this trial demonstrated that the progressive, within-patient olipudase alfa dose escalation regimen was well tolerated in adult ASMD patients. No serious or severe AEs or deaths were reported in the study. Related AEs consisted predominantly of infusion-associated reactions (IARs), most of which were mild in severity with all patients recovering without sequelae. At the end of the 6-month treatment period, a positive response to treatment with olipudase alfa was observed in several individual efficacy parameters. This included mean decreases in spleen and liver volumes by 25.3% and 17.1%, respectively; decreased interstitial lung disease (ILD) scores; increased percent predicted diffusing capacity of the lung for carbon monoxide (DL_{CO}); reduction in serum chitotriosidase, chemokine (CC-motif) ligand 18 (CCL-18), and angiotensin-converting enzyme (ACE); a positive trend

towards a less proatherogenic lipid profile; and, trends for improvement in quality of life assessments for fatigue and pain.

Other clinical studies of olipudase alfa are planned or ongoing. These include:

- A Phase 1/2, multicenter, open-label, ascending-dose study to evaluate the safety, tolerability, PK, PD, and exploratory efficacy of olipudase alfa in pediatric patients aged <18 years with ASMD.
- A Phase 2/3, multicenter, randomized, double-blinded, placebo-controlled repeat-dose study to evaluate the efficacy, safety, PD, and PK of olipudase alfa in patients with ASMD.

A complete summary of nonclinical and clinical experience with olipudase alfa can be found in the investigator's brochure.

4.2 STUDY RATIONALE

Cumulative data from preclinical and human studies conducted to date with olipudase alfa demonstrate both the safety and tolerability of repeat dosing of olipudase alfa. This study will provide long-term data on olipudase alfa in pediatric and adult patients with ASMD.

This study is being conducted to allow patients with ASMD to continue the olipudase alfa treatment they were receiving at the end of their primary study after that study is completed. Individual dose adjustments are allowed in this study, but may also be recommended based on results from completed or ongoing studies of olipudase alfa. The primary objective of this study is to obtain safety data in pediatric and adult patients with ASMD who are exposed to long-term treatment with olipudase alfa. Secondary objectives are to obtain efficacy, PK, and PD data.

Treatment Period

- The current study is an open-label, long-term treatment study planned for 9 years, or until olipudase alfa becomes commercially accessible (see maximum duration below), whichever comes first, unless the patient decides to enter another olipudase alfa clinical trial within the 9-year period prior to when olipudase alfa is commercially accessible.
- The term “commercially accessible” is defined as when olipudase alfa is commercially accessible to each patient on an individual basis (eg, reimbursement being in place). The duration of study treatment with olipudase alfa between local Regulatory approval and commercial accessibility should not exceed 90 days. Therefore, as described below, after local Regulatory approval, the patient can continue in the LTS13632 study for a maximum of 127 days.
- This will ensure 90 days of study treatment with olipudase alfa for patients after local Regulatory approval and a safety follow up phone call 30 to 37 days after the last dose of study treatment.
- Notwithstanding the above, every pediatric patient will be treated in the LTS13632 study for at least 3 years to comply with the agreed PIP.
- The patient can switch immediately after the end of study treatment to commercial treatment without any gap in order to ensure continuity of treatment with olipudase alfa.

5 STUDY OBJECTIVES

5.1 PRIMARY

The primary objective of this study is to obtain data regarding the safety of olipudase alfa in patients with ASMD who are exposed to long-term treatment with olipudase alfa.

5.2 SECONDARY

The secondary objectives of this study are to obtain data regarding the efficacy of olipudase alfa and to characterize olipudase alfa PD and PK following long-term administration.

6 STUDY DESIGN

This is a multinational, multicenter, nonrandomized, open-label, long-term treatment study of approximately 25 patients who have previously participated in a study of olipudase alfa. 5 adult patients rolled over from study DFI13412 into LTS13632 study and approximately 20 pediatric patients are expected to roll over from study DFI13803. Patients will be enrolled directly into this study from their previous study.

Treatment Period

- Enrolled patients will receive an IV infusion of olipudase alfa every 2 weeks for 9 years, or until olipudase alfa becomes commercially accessible (see maximum duration below), whichever comes first, unless the patient decides to enter another olipudase alfa clinical trial within the 9-year period prior to when olipudase alfa commercially accessible.
- The term “commercially accessible” is defined as when olipudase alfa is commercially accessible to each patient on an individual basis (eg, reimbursement being in place). The duration of study treatment with olipudase alfa between local Regulatory approval and commercial accessibility should not exceed 90 days. Therefore, as described below, after local Regulatory approval, the patient can continue in the LTS13632 study for a maximum of 127 days.
- This will ensure 90 days of study treatment with olipudase alfa for patients after local Regulatory approval and a safety follow up phone call 30 to 37 days after the last dose of study treatment.
- Notwithstanding the above, every pediatric patient will be treated in the LTS13632 study for at least 3 years.
- The patient can switch immediately after the end of study treatment to commercial treatment without any gap in order to ensure continuity of treatment with olipudase alfa.

Data Monitoring Committee

A chartered, independent data monitoring committee (DMC) will provide ongoing expert, independent review of safety data to ensure the protection and safety of the patients, as described in [Section 6.4](#).

6.1 DESCRIPTION OF THE PROTOCOL

The study consists of 2 periods, treatment and posttreatment.

6.1.1 Treatment period

Treatment Period

- During the treatment period, patients will receive an IV infusion of olipudase alfa every 2 weeks for 9 years or until olipudase alfa becomes commercially accessible (see maximum duration below), whichever comes first, unless the patient decides to enter another olipudase alfa clinical trial within the 9-year period prior to when olipudase alfa is commercially accessible.
- The term “commercially accessible” is defined as when olipudase alfa is commercially accessible to each patient on an individual basis (eg, reimbursement being in place). The duration of study treatment with olipudase alfa between local Regulatory approval and commercial accessibility should not exceed 90 days.
- Notwithstanding the above, every pediatric patient will be treated in the LTS13632 study for at least 3 years.
- The patient can switch immediately after the end of study treatment to commercial treatment without any gap in order to ensure continuity of treatment with olipudase alfa.

In the first 5 years, safety and efficacy assessments will occur at regular 3, 6, or 12 month intervals then only selected assessments will occur every 6 or 12 months after 5 years.

Schedule of Assessments

In the first 5 years, pharmacodynamic (PD) evaluations will occur every 3 months then every 6 months after the cutoff date for a planned second database lock of the study for purpose of regulatory submissions in 2021. After 5 years, PD evaluations will occur every 12 months.

PK evaluations will occur every 12 months only in the first 5 years and upon introduction of Process C(█) or Process C(█) at any time during the study. Beyond 5 years, pharmacokinetic testing will only occur upon the introduction of Process C(█) or Process C(█). For Process C(█), if treatment is not interrupted, PK sample collection will take place at the patient's last infusion under the current manufacturing scale and at the first infusion under Process C(█). For introduction of Process C(█), if treatment is not interrupted, PK sample collection will take place at the second infusion under Process C(█). In case reintroduction of olipudase alfa coincides with introduction of drug product from Process C(█) or Process C(█), PK samples will be collected at the infusion at which patients receive their usual dose of olipudase alfa under the new process. For schedule of PK assessment in adults, see [Section 1.6, Table 11](#).

6.1.2 Post treatment period

For patients completing or discontinuing/withdrawing from the study, there will be a posttreatment period consisting of an end-of-treatment (EOT) visit 2 weeks (± 7 days) after the last administered dose of study treatment and a safety follow-up phone call 30 to 37 days after the last administered dose of study treatment.

An EOT visit and a safety follow-up phone call will also apply in case the patient switches immediately after the end of study treatment to commercial treatment.

6.2 INTERIM ANALYSIS

No formal interim analysis is planned for this study. A formal summary of data or interim CSR may be produced to support regulatory approval(s) and/or other submission/application requirement(s).

6.3 DURATION OF STUDY PARTICIPATION

The length of a patient's participation will be from the time the informed consent form is signed until the last planned assessment/visit. The approximate maximum study duration per patient is as follows:

- Treatment period of 9 years or until olipudase alfa becomes commercially accessible (see maximum duration below), whichever comes first, unless the patient decides to enter another olipudase alfa clinical trial within the 9-year period prior to when olipudase alfa is commercially accessible.
- The term “commercially accessible” is defined as when olipudase alfa is commercially accessible to each patient on an individual basis (eg, reimbursement being in place). The duration of study treatment with olipudase alfa between local Regulatory approval and commercial accessibility should not exceed 90 days. Therefore, as described below, after local Regulatory approval, the patient can continue in the LTS13632 study for a maximum of 127 days.
- This will ensure 90 days of study treatment with olipudase alfa for patients after local Regulatory approval and a safety follow up phone call 30 to 37 days after the last dose of study treatment.
- The patient can switch immediately after the end of study treatment to commercial treatment without any gap in order to ensure continuity of treatment with olipudase alfa.
- Notwithstanding the above, every pediatric patient will be treated in the LTS13632 study for at least 3 years.
- Follow up period concluded with a safety follow up phone call 30 to 37 days after the patient's last infusion in the LTS13632 study. A safety follow-up phone call will also apply in case the patient switches immediately after the end of study treatment to commercial treatment.

6.3.1 Determination of end of clinical trial (all patients)

The study will be considered to be complete when the last patient has his/her last contact with his/her study site.

6.4 STUDY COMMITTEES

An independent DMC, composed of members independent from the sponsor and the study investigators, is implemented in order to monitor patient safety by conducting formal reviews of accumulated safety data. The DMC will provide the sponsor with appropriate recommendations on the conduct of the clinical trial to ensure the protection and safety of the patients enrolled in the study (ie, exposure to study drug). All activities and responsibilities of the DMC are described in the DMC charter in compliance with applicable guidance ([7](#)).

Data monitoring committee meetings will occur at regular intervals as outlined in the DMC charter specific to this study. The report of a potential dose-limiting toxicity to the sponsor or the occurrence of any safety-related issues identified by the sponsor's medical monitor or global safety officer that pose a medical concern, for example a fatal event, will result in the DMC holding an ad hoc review of the safety data and providing its recommendations to the sponsor regarding further patient treatment.

7 SELECTION OF PATIENTS

7.1 INCLUSION CRITERIA

To enter this study, patients must have fulfilled the following criteria:

- I 01. The patient completed the treatment period of a previous study of olipudase alfa with an acceptable safety profile in the opinion of the investigator and sponsor.
- I 02. The patient and the patient's parent(s)/legal guardian(s) is willing and able to provide signed written informed consent.
- I 03. The patient who is female and of childbearing potential must have a negative urine pregnancy test for beta-human chorionic gonadotropin (β-HCG) (see [Section 9.1.9](#)).
- I 04. Female patients of childbearing potential and sexually mature male patients must be willing to practice true abstinence in line with their preferred and usual lifestyle or use 2 acceptable effective methods of contraception up to 15 days following their last dose of study drug (see [Section 10.2.3.2](#)).

7.2 EXCLUSION CRITERIA

Patients who have met all the above inclusion criteria listed in [Section 7.1](#) will be assessed for the following exclusion criteria:

7.2.1 Exclusion criteria related to study methodology

- E 01. The patient has any new condition or worsening of an existing condition which in the opinion of the investigator would make the patient unsuitable for enrollment, or could interfere with the patient participating in or completing the study.
- E 02. The patient, in the opinion of the investigator, is unable to adhere to the requirements of the study.
- E 03. The patient is unwilling or unable to abstain from the use of alcohol for 1 day prior to and 3 days after each olipudase alfa infusion for the duration of the treatment period.
- E 04. The patient is unwilling or unable to avoid, for 10 days before and 3 days after liver biopsies, medications or herbal supplements that are potentially hepatotoxic (eg, 3-hydroxy-3-methylglutaryl-coenzyme A reductase inhibitors, erythromycin, valproic acid, antidepressants, kava, echinacea) or may cause or prolong bleeding (eg, anticoagulants, ibuprofen, aspirin, garlic supplements, ginkgo, ginseng) (only patients who previously participated in the DFI13412 study).

7.2.2 Exclusion criteria related to the current knowledge of the compound and condition

- E 05. The patient requires medication(s) that may decrease olipudase alfa activity (eg, fluoxetine, chlorpromazine; tricyclic antidepressants [eg, imipramine, desipramine]).

8 STUDY TREATMENTS

8.1 INVESTIGATIONAL MEDICINAL PRODUCT(S)

The study drug, olipudase alfa, is a sterile, white to off-white lyophilized cake supplied in single-use, 20 cc Type 1 glass vials. Each vial contains 20 milligrams of extractable olipudase alfa.

The study drug will be reconstituted with 5.1 mL of sterile water for injection to yield a concentration of 4.0 mg/mL of olipudase alfa. The study drug will be further diluted in 0.9% sodium chloride for injection solution to a specific volume based on dose.

Detailed instructions on olipudase alfa preparation, storage, and administration are provided in the corresponding manual.

Refer to [Section 8.5](#) for product handling and complaints reporting.

8.1.1 Treatments administered

Patients will receive olipudase alfa every 2 weeks (± 3 days). Home infusions may be possible. To be eligible for home infusions, patients must meet the criteria in [Section 10.2.1](#).

Patients will start this study at the same dose they were receiving at the end of their primary study, provided that they have not missed more than 1 biweekly dose between studies.

All patients will have a visit 2 weeks (± 3 days). Quarterly visits will occur at the site. If the site visit is not possible due to site closure or extenuating circumstances that prevent an in-person site visit (eg, during COVID-19 pandemic) and home infusion is already approved for the eligible patient, quarterly visits will be done at home. Quarterly visit specific assessments that need a site visit will not be done at that time and will be done as unscheduled as soon as site visits become available. In such a case, some of the quarterly visit assessments may be done by home nurse (eg, lab sampling) and by the site through the phone (eg, Health-related quality of life instruments). Telehealth visits are an acceptable alternative to site visits, if site visits are not possible during a regional or national emergency declared by a governmental agency such as the COVID-19 pandemic due to site closure or extenuating circumstances that prevent an in-person site visit, in accordance with institutional policy and with applicable country-specific regulations.

Dose reintroduction regimens may be required for patients who have missed more than 1 dose between studies or during this study (LTS13632), depending on their usual dose. For patients receiving home infusions who have missed 2 or fewer doses, the investigator can decide whether reintroduction should occur at the hospital/study site or via home infusion. For patients who have missed 3 or more doses ≥ 0.6 mg/kg, reintroduction of olipudase alfa should occur at the hospital/study site. If the site visit is not possible during a regional or national emergency declared

by a governmental agency such as the COVID-19 pandemic due to site closure or extenuating circumstances that prevent an in-person site visit, reintroduction may be done via home infusion.

Olipudase alfa reintroduction guidance will depend on the patient's usual dose and the number of missed infusions:

- If a patient misses 1 dose, continue at the dose previous to the missed dose.
- If a patient misses 2 doses:
 - If the previous dose was >0.6 mg/kg, the next dose must be 1 level below the last dose,
 - If the previous dose was ≤ 0.6 mg/kg, the next dose must be equal to the last dose.
- If a patient misses 3 or more doses:
 - If the previous dose was >0.6 mg/kg, the next dose must be 0.3 mg/kg (0.3 mg/kg should be repeated at the subsequent infusion, similar to dose escalation schedule in the original study). Details will be provided in the study manual
 - If the previous dose was ≤ 0.6 mg/kg, the next dose must be equal to the last dose,
 - If a patient has missed 3 or more doses ≥ 0.6 mg/kg, reintroduction of olipudase alfa for patients receiving infusions at home should occur at the hospital/study site.
 - If the site visit is not possible during a regional or national emergency declared by a governmental agency such as the COVID-19 pandemic due to site closure or extenuating circumstances that prevent an in-person site visit, reintroduction may be done via home infusion, if the patient has previously been approved for home infusion.

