10.4.1 Temporary treatment discontinuation with investigational medicinal product(s)

Temporary treatment discontinuation, decided by the investigator, corresponds to more than 1 dose not administered to the patient. Dose reintroduction regimens may be required for patients who have missed more than 1 dose between studies, depending on their usual dose.

For patients receiving home infusions who have missed 2 or fewer doses, the investigator can decide whether reintroduction should occur at the hospital/study site or via home infusion. For

patients who miss 3 or more doses ≥ 0.6 mg/kg, reintroduction of olipudase alfa should occur at the hospital/study site. If the site visit is not possible due to site closure or extenuating circumstances that prevent an in-person site visit (eg, during COVID-19 pandemic), reintroduction may be done via home infusion.

The investigator, in consultation with the sponsor, will determine whether the patient will be redosed. Reintroducing patients to olipudase alfa treatment will take into account the patient's usual dose, the number of missed infusions, and the patient's ability to tolerate the dose.

Upon reintroduction of treatment, certain assessments will be repeated at infusions ([Section 8.1.5](#)). The investigator will decide if additional specific assessments may be required before the patient can begin the reintroduction regimen.

Olipudase alfa reintroduction guidance is described in [Section 8.1.1](#). Reintroduction of olipudase alfa treatment will be done with appropriate monitoring at the discretion of the investigator and confirmation that the patient still meets the study criteria ([Section 7.1](#) and [Section 7.2](#)).

The duration of all temporary treatment discontinuations should be recorded by the investigator in the appropriate screens of the CRF.

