Cytokine release syndrome is another type of IAR, attributed to the release of excessive amounts of cytokines shortly after the IV administration of certain therapeutic agents. The severe form of CRS is cytokine storm, which may be life threatening. Nonclinical studies of high-dose olipudase alfa have suggested the possibility of CRS. There were no events characterized as cytokine release syndrome in either the Phase 1 single- or the Phase 1b repeat-dose trials with olipudase alfa (5, 6). The Phase 1 single-dose study demonstrated increases in IL-8 and IL-6; macrophage inflammatory protein 1, alpha component (MIP-1 α); macrophage inflammatory protein 1, beta component (MIP-1 β); and other cytokines and biomarkers (based Myriad Rules-Based Medicine Human Multi-Analyte Profile® antigen panel) after a single dose of ≥ 0.3 mg/kg of olipudase alfa (5). In the Phase 1b trial, increases in mean IL-6 and IL-8 values were associated with the first administrations of olipudase alfa at doses 0.6 mg/kg through 2.0 mg/kg and tended to be concurrent with acute phase responses (6). Unlike immunoglobulin-mediated hypersensitivity reactions, no prior antigen exposure is required for the development of CRS. Symptoms of CRS develop soon after exposure, and range from mild to severe. Although CRS shares some symptoms with other IARs (ie, hypersensitivity reactions and APRs), symptoms typical of CRS include pyrexia, nausea, vomiting, fatigue, pain, myalgia, and in severe cases, multiorgan system dysfunction or failure, severe headache, and pulmonary edema. Cytokine release syndrome will be determined based on combined significant laboratory findings and clinical symptoms.

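### After three or more missed infusions, Protocol 8.1.1 restarts a patient last on 0.6 mg/kg at twice the dose given to a patient last on 1.0 to 3.0 mg/kg

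*Protocol*

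**What the plan says.** Section 8.1.1 of the Protocol gives reintroduction rules by number of missed infusions and previous dose. For three or more missed infusions there are two cases:

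- For a previous dose above 0.6 mg/kg, "the next dose must be 0.3 mg/kg (0.3 mg/kg should be repeated at the subsequent infusion", a sequence described as "similar to dose escalation schedule in the original study".
- "If the previous dose was ≤ 0.6 mg/kg, the next dose must be equal to the last dose".

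The same branch also says that home-infused patients who missed three or more doses of 0.6 mg/kg or higher should be reintroduced at the hospital or study site. Here exactly 0.6 falls on the cautious side.

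For two missed infusions, a previous dose above 0.6 mg/kg drops by one level, and a dose of 0.6 or below is resumed unchanged.

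The clinical trial summary, Section 1 and Section 8.1.5 repeat the rule on where reintroduction takes place but give no restart dose. Section 10.4.1 points back: "Olipudase alfa reintroduction guidance is described in" Section 8.1.1.

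**The concern.** The 0.3 mg/kg restart treats a long gap as needing stepwise re-exposure. On that reasoning, a patient who had reached only 0.6 mg/kg has no less need of a step down than one who had reached 3.0. Yet the patient at 0.6 is the only one above 0.3, among the named dose levels, who resumes at full dose.

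The background supports caution near this level, within limits. Section 4.1 links toxicity in the mouse model to the rate of substrate breakdown and suggests that gradual removal reduces it. For the Phase 1b trial, the cytokine release part of Section 10.5.1.3.2 reports that "increases in mean IL-6 and IL-8 values were associated with the first administrations of olipudase alfa at doses 0.6 mg/kg through 2.0 mg/kg". That evidence concerns first doses, not restarts. The single-dose study saw cytokine rises from 0.3 mg/kg, so 0.3 is a lower step and not a risk-free one.

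There is also a plausible route to the problem. Section 8.1.6 stops dosing temporarily for related serious events or liver-test rises. If that happens at 0.6 mg/kg and three or more infusions are missed, 8.1.1 read literally requires the patient to resume at the very dose at which treatment was stopped.

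**Working it through.** **Inputs**

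- Restart rules: Section 8.1.1, as quoted.
- Dose levels: Section 4.1 gives "Single doses of 0.03, 0.1, 0.3, 0.6, and 1.0 mg/kg of olipudase alfa were infused sequentially" for the single-dose study, and a Phase 1b escalation from 0.1 to a target of 3.0 mg/kg. The cytokine release text in Section 10.5.1.3.2 adds 2.0 mg/kg.
- Assumption: these are the relevant levels. The full escalation schedule is not in the documents.

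**Rules as functions of last dose d (mg/kg)**

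- Three or more missed, as written: r(d) = 0.3 if d > 0.6; r(d) = d if d ≤ 0.6.
- Three or more missed, amended: r(d) = 0.3 if d ≥ 0.6; r(d) = d if d < 0.6.
- Two missed, as written: one level below d if d > 0.6; d otherwise.

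| Last dose | 3+ missed, as written | 3+ missed, amended | 2 missed, as written |
|---|---|---|---|
| 0.03 | 0.03 | 0.03 | 0.03 |
| 0.1 | 0.1 | 0.1 | 0.1 |
| 0.3 | 0.3 | 0.3 | 0.3 |
| 0.6 | **0.6** | 0.3 | 0.6 |
| 1.0 | **0.3** | 0.3 | 0.6 |
| 2.0 | 0.3 | 0.3 | 1.0 |
| 3.0 | 0.3 | 0.3 | 2.0 |

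**Check:** a higher last dose should never give a lower restart dose.

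- Three or more missed, as written: fails once, between 0.6 and 1.0. The ratio is 0.6 / 0.3 = 2.
- Three or more missed, amended: holds at every level.
- Two missed, as written: holds at every level, so that branch needs no change.

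**Cost to an affected patient,** assuming 0.6 follows the repeated 0.3:

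- Delay in returning to 0.6: 2 infusions × 2 weeks = 4 weeks.
- Drug forgone: 2 × (0.6 − 0.3) = 0.6 mg/kg.

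**Limit of the operator change:** a last dose strictly between named levels, say 0.45 mg/kg after an individual adjustment, would still restart at 0.45, above the 0.3 given to higher-dose patients. The current rule does the same, so the change does not make this worse.

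**The case against.** The strongest counter-argument is reach. Section 4.1 says all five Phase 1b adults stayed at 3.0 mg/kg, so they entered in the >0.6 group, and nothing places a pediatric patient on a stable 0.6. For a patient interrupted during re-escalation, 8.1.1 introduces the guidance by reference to the usual dose although its branches refer to the previous dose. On the usual-dose reading, a 3.0 mg/kg patient stopped at 0.6 already restarts at 0.3. This stands as a limit on frequency: the documents show no such patient and leave the mid-escalation reading open.

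Second, there are safeguards. A patient at 0.6 should restart on site, barring an emergency; Section 8.1.5 adds monitoring around reintroduction infusions; Section 8.1.4 allows dose changes discussed with the sponsor; and Section 10.4.1 has investigator and sponsor weigh tolerability before redosing. These soften the consequence, but 10.4.1 returns to 8.1.1 for the dose, and the wording there is *must*. Section 8.1.5 monitoring also runs until the usual dose is reached, so whether it covers a patient whose usual dose is 0.6 and who restarts there is arguable.

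Third, nothing shows that resuming 0.6 after a gap is harmful, and the study manual, which 8.1.1 cites for details, was not available. Both points are fair. The case rests on the protocol's own logic, not on demonstrated harm, and no section gives a reason for exempting 0.6.

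**Conclusion.** The concern holds. In the current text, one boundary value is on the wrong side: after three or more missed infusions, a patient last on 0.6 mg/kg restarts at 0.6, and a patient last on 1.0 to 3.0 restarts at 0.3. The twofold reversal follows from Section 8.1.1 alone; the amendment history is not needed to show it.

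The conclusion that 0.6 is the only level affected assumes the dose levels named in the documents. Confidence is medium, because the full escalation schedule and the study manual were not seen. The case is probably uncommon and its frequency cannot be estimated from the documents. This is a dosing-rule error with a possible safety consequence for an individual patient; no planned analysis or sample size changes. It is worth correcting at the next amendment.

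**What to change.** In the branch of Section 8.1.1 for three or more missed doses, and only there:

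- change >0.6 mg/kg to ≥0.6 mg/kg for the restart at 0.3 mg/kg, repeated once;
- change ≤0.6 mg/kg to <0.6 mg/kg for the restart at the last dose.

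Leave the two-missed branch and the ≥0.6 site rule alone. Sections 1, 8.1.5, 10.4.1 and the summary need no edit. Align the study manual if it repeats this branch. If individually adjusted doses between 0.3 and 0.6 mg/kg are in use, a first restart dose defined as the lower of the last dose and 0.3 mg/kg would cover them too. If the sponsor means to exempt 0.6, the protocol should say why.

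The drafting cost is one pair of operators. For an affected patient, the cost is the delay and reduced dose worked out above, with the Section 8.1.5 assessments at both 0.3 infusions. In children, that sampling has to fit the limit in Section 9.5 of 7 mL/kg in any 8 weeks.
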